**9.8. Data Review**

Prior to unblinding of the study database, the data will be reviewed by the Clinical Project Manager. The investigational centers will be queried about any discrepancies or unclear data and, if necessary, these will be corrected in the database.

**9.9. Derived Data**

The following data will be derived from collected data:

- [Redacted] CCI
  - | [Redacted] CCI
  - | [Redacted] CCI
  - | [Redacted] CCI
- | [Redacted] CCI
  - | [Redacted] CCI
  - | [Redacted] CCI
  - | [Redacted] CCI
- [Redacted] CCI
- | [Redacted] CCI
  - | [Redacted] CCI
  - | [Redacted] CCI
- | [Redacted] CCI
  - | [Redacted] CCI
  - | [Redacted] CCI
- | [Redacted] CCI
- | [Redacted] CCI
  - | [Redacted] CCI
  - | [Redacted] CCI
- | [Redacted] CCI
  - | [Redacted] CCI
  - | [Redacted] CCI
  - | [Redacted] CCI

**9.10. Transformed Data**

No data transformations are planned.

**9.11. Changes from Protocol Planned Analysis**

The protocol included collecting information on the reason for use of rescue drugs (secondary objective #7), however, it was determined at the time of CRF development that capturing such data would not add to the determination that a rescue medication was given. Therefore, this was not captured.

The sample size justification in the protocol was not updated to match the final methodology used. While both the protocol and the SAP sample size justifications results in the need for 127 subjects per treatment arm, the assumptions in this SAP are more indicative of the actual assumptions and methodology used to arrive at this sample size.

The protocol did not make provisions for subjects who needed to be hospitalized or kept in the ED overnight for observations. The SAP covers the needs to treat the time spent at the treatment center to “missing” for these subjects.

**10. STUDY POPULATION****10.1. Subject Accountability**

The disposition of all subjects, including those who discontinued, will be summarized by treatment group, using frequencies and percentages in each population. Subjects will be categorized into ITT, SAF, and PP populations. Screen failures and excluded-prior-to-enrollment will not be summarized.

**10.2. Protocol Deviations**

All randomized subjects will be included in the ITT and SAF populations. If a violation hinders the ability to assess an efficacy outcome, the following approaches can be taken:

Examples:

- i) If patient does not have the disease intended to treat, the outcome for the 2 hr assessment will be set to the baseline values and the subjects will be considered a treatment failure. In this example, the “readiness for discharge” time will be missing, since the discharge time is confounded by the wrong disease.
- ii) if a subject receives an antihistamine within 2 hrs prior to baseline (not meeting exclusion #4), that subject will be considered a failure with change from baseline to 2 hr pruritus score and with change from baseline to 2 hr extent of urticaria score set to zero (0). In this example, sedation score will be missing since sedation is confounded by the antihistamine prior to baseline.

---

Inclusion of subjects in other efficacy endpoints will be dependent on availability of data for each assessment times point. Subject data will be reviewed for major protocol violations by a qualified clinical reviewer prior to database lock and unblinding. Subjects with any major protocol violations will be identified and excluded from the Per Protocol Population. A summary list of the individual subjects excluded, will be provided, sorted by treatment group with description of their protocol violation/deviation.

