Before discharge, patients will be instructed that a member of the site staff will telephone them at approximately the same time or the next convenient time (e.g.: if patient is discharged at 3 am, the site staff will telephone the patient at ~8 am) the following day, and the day after (i.e. ~24 hours, and ~48 hours later) to ask them a few short questions to follow up on the treatment of their acute urticaria (See [attachment C](#)). Patients will be asked to provide contact telephone number where they can be reached and also given a telephone number for them to call in the event that they are not contacted. Patients will also be instructed to call this number to report any AEs or SAEs they may have experienced.

The decision to discharge the patient (Time of "Readiness for Discharge") can be taken by the Investigator/designee provided the following criteria are met:

- 1) Symptoms of the acute allergic reaction have been effectively treated based on investigator/designee's opinion (*Note: if rescue drugs are used, patients are deemed not effectively treated by the study drug, but effectively treated by rescue drugs.*)
- 2) Patient is alert enough (sedation scores = 0) to understand Discharge Instructions
- 3) Based on the investigator's judgment, the patient is fit to be discharged

Note:

- i) *If patient is fit to be discharged, but not alert enough to drive home when the sedation score is at "1" or higher, he/she may be kept for a maximum of 5 hours (to make it practical for research personnel). But appropriate arrangement must be done, such as: call for a taxi, arrange a friend or relative to help drive, or ask patient to stay in the waiting room until sedation goes away, etc.*
- ii) *Standard discharge instruction should be given. If medications are prescribed at discharge, instruct patients take them "as needed"*
- iii) *In the event if the symptoms were not effectively treated, patients will be treated following the standard of care by attending physician.*
- iv) *If "Time of Readiness for Discharge" happens prior to the 2 hour assessment, the "patient Pruritus Score" must be Zero, otherwise the patient has to be kept in the treatment center for at least 2 hours.*

All AEs and SAEs that are reported after the patient signs an ICF will be recorded in the source documents and/or captured in the CRF.

Study procedures and their timing are summarized in the Study Schedule, Protocol [Attachment A](#).

5. Study Population

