## 7. ANALYSIS POPULATIONS

The disposition of all subjects, including those who discontinued, will be summarized by group, using counts and frequencies in each population. Subjects will be categorized into the following analysis populations:

**Intent-To-Treat (ITT) Population:** Includes any subject who was randomized and given a Subject ID Number with intent to treat with one of the blinded study drugs. All efficacy and non-inferiority analyses will be performed on the ITT population with subjects grouped by the treatment they were randomized to receive.

---

**Safety Population (SAF):** Includes any subjects in the ITT population who actually receives a blinded study drug, regardless whether or not they complete all assessments, withdraw or are discontinued by the investigator. All safety summaries will be performed on the SAF population with subjects grouped by the treatment they actually received.

**Per Protocol Population (PP):** Includes subjects in the SAF population who complete all necessary assessments without any incidence that would potentially affect the ability to objectively assess treatment response (e.g. discontinuation, protocol deviation, use of rescue medication, etc.).

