### **9.3. Adjustments for Multiplicity**

There is only one primary endpoint being tested to determine efficacy of cetirizine 10 mg/mL injection on 2hr patient rated pruritus severity. Key secondary endpoints will be used to support the claims of the primary efficacy outcome. There are 2 outcome measures that are key in supporting the efficacy claim: the need to return to treatment center after study discharge and time spent at the treatment center (time from treatment administration to readiness for discharge). Family-wise error rate will be controlled using Holm-Bonferroni method of rejecting individual hypotheses ([Holm, 1979](#)).

Although nominal p-values will be reported for treatment differences, none of the other secondary endpoints will be used to evaluate for superiority or non-inferiority of cetirizine compared to diphenhydramine, therefore no adjustments for multiplicity are planned.

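### SAP 10.2(i) lets a recorded readiness-for-discharge time be set to missing for patients judged not to have the intended disease, on a judgement not tied to pre-dose information

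*SAP*

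**What the plan says.** SAP 9.3 names two key secondary outcomes, return to a treatment centre and time from dosing to readiness for discharge, and controls the error rate across them by Holm's method. SAP 7 fixes the population: "All efficacy and non-inferiority analyses will be performed on the ITT population with subjects grouped by the treatment they were randomized to receive". Protocol 6.5 likewise puts everyone who was dosed into all analyses.

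SAP 10.2 covers violations that get in the way of assessing an efficacy outcome and introduces its examples with "the following approaches can be taken". In example (i) the patient does not have the disease under treatment. The patient stays in ITT, and "the outcome for the 2 hr assessment will be set to the baseline values and the subjects will be considered a treatment failure". For the same patient, the readiness-for-discharge "time will be missing, since the discharge time is confounded by the wrong disease". The section then makes inclusion in other efficacy endpoints depend on available data, and has a clinical reviewer check for major violations before lock and unblinding.

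Elsewhere the SAP gives one other reason for a missing time. Under SAP 2, patients who are admitted or stay overnight have no readiness time recorded and are left out of the summary. SAP 9.11 declares this as a departure: "The protocol did not make provisions for subjects who needed to be hospitalized or kept in the ED overnight for observations". It does not mention wrong-disease patients.

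**The concern.** The admission rule deals with a time that was never recorded. Example (i) can override a time that was, since Protocol 4 has the time of readiness written in the source documents.

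The documents give no criterion, assessor or cut-off time for the wrong-disease judgement itself. Protocol 5.3 expects some eligibility violations to come to light after dosing. Protocol 5.3 and 6.4.5 also infer from an early need for rescue that a patient should not have passed screening, so the post-dose course can feed an eligibility judgement. If poor response or a long stay prompts a second look at the diagnosis, removal depends on outcome. If that happens more often in one arm, the time comparison is shifted.

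At stake is a multiplicity-controlled claim that would be labelled ITT but rest on a subset settled after randomisation. The primary analysis is not affected by this sentence.

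**Working it through.** **Does the patient leave the comparison?**

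1. SAP 10.2(i) sets the time to missing.
2. The carry-forward rules in SAP 9.1 cover pruritus, extent of urticaria and sedation. They do not cover time.
3. SAP 10.2 makes inclusion in non-primary efficacy endpoints depend on available data.
4. Unless SAP 11.2 says otherwise, the patient therefore drops out of the time analysis. The contents page lists 11.2, but the public text passes from 11.1 to 11.3, so this step is an inference.

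**Figures in the plan.** The documents give no expected time at centre, no SD for it and no expected number of wrong-disease patients. The only size to work from is 127 per arm (SAP 9.11). It was set for the primary outcome, and its SD and alpha are redacted. With the margin of 0.50 and 90% power it implies an SD of about 1.23 at one-sided 0.025 or 1.36 at one-sided 0.05, so it is attainable but cannot be confirmed. It is taken as given here.

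**Shift in an arm mean.** Assumed, not from the documents: the rest of the arm averages 120 min and the removed patients 300 min.

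- Shift for k deletions = (300 − 120) × k / 127.
- k = 4: (123 × 120 + 4 × 300) / 127 = 15,960 / 127 = 125.7 min, against 120.0 after deletion, a shift of 5.7 min.
- k = 1 gives 1.4 min and k = 6 gives 8.5 min.
- With 6 deleted in one arm and 2 in the other, the difference moves by 4 × 180 / 127 = 5.7 min.

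**Power.** Assumed: a comparison of means at the first Holm step, 0.05 / 2 = 0.025 two-sided, and a true effect giving 90% power with 127 per arm. That effect is (2.241 + 1.282) × √(2/127) = 0.442 SD. Dropping 1, 3, 6 or 13 per arm leaves power of 89.8%, 89.3%, 88.4% or 86.4%. Loss of patients as such matters little.

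**Error rate under unequal removal.** Let E be the excess time of removed over retained patients, in SDs. The shift is b = (difference in numbers removed / 127) × E, and the standard error is √(2/127) = 0.1255 SD. With no true difference among all randomised patients, the rejection probability is 1 − Φ(2.241 − |b|/0.1255) + Φ(−2.241 − |b|/0.1255).

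- Equal numbers and equal E: b = 0, rejection 0.025.
- 1 v 3 removed: b = 0.016, 0.031 and 0.047 SD for E = 1, 2 and 3; rejection 0.026, 0.030 and 0.036.
- 1 v 6 removed: b = 0.039, 0.079 and 0.118 SD; rejection 0.032, 0.055 and 0.098.

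If the removed patients had shorter stays, E is negative and the shift changes sign.

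**The case against.** The other side has good points.

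- **The rule is permissive.** It is one of several examples and applies only where a violation hinders assessment. This stands, but case-by-case discretion is itself a weakness for an error-controlled endpoint.
- **Review precedes unblinding in a double-blind trial.** This stands against selection by known arm. It does not stop removal that depends on response, which can differ between arms without anyone knowing the allocation.
- **An ITT population does not promise a value for every endpoint.** True, and SAP 2 already leaves some patients out. Those patients have no time; here a recorded time can be discarded.
- **Few patients are likely to be affected.** Eligibility is verified before randomisation (Protocol 4). Some wrong-disease patients may also have been admitted or discontinued and so have no time to discard. This limits the size of the problem.
- **Losses would be partly visible.** SAP 9 reports the number of non-missing values, and SAP 10.2 lists per-protocol exclusions by arm. Neither shows whether a judgement used pre-dose information only.

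A reader might infer three stronger points that the documents do not support. The first is that scoring the patient as a failure at 2 hours while leaving the time missing is contradictory in itself. A change score has a natural failure value (zero) and a time does not, so different handling can be defended.

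The second is that example (ii) exposes an inconsistency. There "sedation score will be missing since sedation is confounded by the antihistamine prior to baseline", and Protocol 4 lists as a discharge criterion "Patient is alert enough (sedation scores = 0) to understand Discharge Instructions", yet the discharge time is kept. But note (i) to those criteria describes a patient who is fit for discharge with a sedation score of 1 or more, so the documents do not settle that sedation determines readiness.

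The third is that the rule removes non-responders or favours one drug. The rule turns on disease, not response, and a wrong-disease patient could also leave early.

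**Conclusion.** The concern holds in a limited form. SAP 10.2(i) allows a recorded readiness time to be discarded on a judgement not confined to pre-dose information. On the visible text the patient then leaves a Holm-controlled comparison that SAP 7 places on the ITT population. SAP 9.11 does not declare this.

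The documents do not allow the effect to be sized. Loss of power is minor. The risk is bias from unequal, outcome-related removal, in a direction that cannot be stated. The minute shifts and error rates above rest on assumed counts and times and on a comparison of means that the public text does not confirm; they are not estimates for this trial. The wording should be corrected, but the point does not threaten the primary conclusion.

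**What to change.** In SAP 10.2(i), replace the sentence on the readiness time with wording to this effect: *In the ITT analysis of time at the treatment centre, every recorded readiness-for-discharge time is used, including those of patients with eligibility violations. Patients judged not to have the intended disease are left out only in the per-protocol analysis or a stated sensitivity analysis. Their number is reported by arm, with whether each judgement used pre-dose information only.* Check that SAP 11.2 agrees.

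Patients with no recorded time because they were admitted or kept overnight are outside this change; SAP 2 and 9.11 govern them.

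The cost is a sentence or two of SAP text, a small by-arm tabulation, and a note of the basis for each judgement. No new clinical measurement is needed. The downside is that a few retained times will reflect another condition and add slight noise.

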The objectives and purpose of the study will be described to subjects presenting at the participating clinical centers. If a subject agrees to participate in the study, an informed consent form (ICF) will be signed by the subject according to the process followed by each center for obtaining informed consent. After consent is received, the study investigator or designee will verify all inclusion and exclusion criteria to ensure patient eligibility and capture all baseline data such as baseline urticarial symptom scores, vital signs, age, previous medical history, cause of the symptoms (if known), and prior medication use, including all medication taken prior to coming to the facility. Once these data have been collected, the patient will be randomized to receive either cetirizine injection or diphenhydramine injection. The time that the study medication is administered will be recorded in the source documents and/or in the eCRF.

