5.3 Discontinuations

Subjects have the right to withdraw from the study at any time for any reason without compromising their clinical management. The investigator also has the right to withdraw subjects from the study if he/she feels it is the best interest of the subject, or if the subject is uncooperative or non-compliant. The discontinued patients will be followed to resolution of any ongoing AEs.

Reasons for discontinuation include:

- Violation of Inclusion or Exclusion criteria found after the study medication has been administered
- The investigator, patient, or the health care professional performing assessments, become un-blinded to the study medication for whatever reason;
- The investigator decides that the patient should be withdrawn. If this decision is made because of a serious adverse event, the study drug, if any, is to be discontinued and appropriate measures are to be taken. The investigator will notify the Sponsor immediately;
- Administrative decision by the Sponsor or Regulatory Authorities. All patients will be discontinued from the protocol and notified of the reasons for the discontinuation;
- The subject may withdraw from the study for any other reason, including withdrawal of consent.

An excessive rate of withdrawal can make the study results difficult to interpret. Any patient who discontinues for a reason other than the occurrence of an adverse event will be replaced by enrolling an additional patient.

The reason for any discontinuation will be fully documented on the Source Document and/or CRF.

Should a patient decide to withdraw, every effort will be made to complete and report all study observations, particularly the 24 hour and/or 48-hour follow-up, as thoroughly as possible. The investigator/designee should contact the subject either by telephone, or through a personal visit if necessary, to determine as completely as possible the reason for the withdrawal.

Note:

- *After discharge, two follow-up phone calls are planned at ~24 hours and ~48 hours. However, sometimes patients do not like to answer phone calls. It is possible only one follow-up can be obtained. In this case, this patient is not considered as discontinued or as protocol deviation.*

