### **9.6. Premature Discontinuation and Missing Data**

For any subject who withdraws prematurely from the study, all available data up to the time of discontinuation will be included in analyses.

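### SAP 10.2 sets the 2-hour pruritus change to zero for two kinds of ineligible patient in the ITT non-inferiority test; in expectation this shrinks a true deficit, though probably by little

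*SAP*

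**What the plan says.** SAP 7 and 9.1 place the primary and non-inferiority analyses on the ITT population. SAP 11.1 sets the margin at -0.50 on the mean change from baseline in patient-rated pruritus at 2 hours (D2).

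SAP 10.2 retains all randomised patients and introduces its handling of violations with "If a violation hinders the ability to assess an efficacy outcome, the following approaches can be taken". Two examples follow:

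- Wrong disease: "the outcome for the 2 hr assessment will be set to the baseline values and the subjects will be considered a treatment failure".
- Antihistamine within 2 hours before baseline (exclusion 4): "that subject will be considered a failure with change from baseline to 2 hr pruritus score" set to zero.

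The same section covers the per-protocol set: "Subjects with any major protocol violations will be identified and excluded from the Per Protocol Population". The review that identifies them takes place before unblinding.

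Two other places bear on the same patients. Protocol 5.3 lists among its reasons for discontinuation "Violation of Inclusion or Exclusion criteria found after the study medication has been administered". SAP 9.6 says that for patients who withdraw early "all available data up to the time of discontinuation will be included in analyses".

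**The concern.** Scoring an ineligible patient as a failure looks conservative, and in a superiority trial it usually is. In a non-inferiority trial, giving the same value to patients in both arms pulls the two means together. If cetirizine is truly worse by the margin, that moves the expected difference toward the claim. The overwritten values enter the primary test directly.

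The two examples are not alike. Patients who took an antihistamine beforehand still have urticaria, so their recorded scores may carry a treatment difference that the rule erases. Patients with the wrong disease may show little difference between the drugs anyway, so their recorded scores could dilute the comparison just as much.

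There is also an overlap between rules. Take a violator whose 2-hour score was recorded and who was then discontinued under protocol 5.3. SAP 9.6 brings in the recorded score; SAP 10.2 puts in zero.

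**Working it through.** **Inputs from the documents.** Margin -0.50 (SAP 11.1); two-sided 95% limits (SAP 9); 90% power (SAP 6); and 127 per arm, since SAP 9.11 says the calculation "results in the need for 127 subjects per treatment arm".

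**Inputs assumed.** The SD and the sample-size alpha are redacted, and the share f of zeroed patients is not given. With 127 per arm, margin 0.50, 90% power, zero true difference and one-sided 2.5%, a t-based calculation gives SD = 1.224. One-sided 5% would give 1.358. The planned 127 therefore cannot be confirmed independently; it serves here only to back-solve the SD. The comparator mean reduction is taken as 1.5. The difference is cetirizine minus diphenhydramine in mean reduction, so negative is worse.

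**Formulas.** A share f of each arm is set to D2 = 0:

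- Expected difference = (1-f) × true difference.
- Arm variance = (1-f) × SD² + f(1-f) × (arm mean)².
- SE = √[(variance C + variance D)/127].
- P(non-inferiority) ≈ 1 - Φ(1.96 - (expected difference + 0.50)/SE).

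**Example, f = 5%, true difference -0.50 (means 1.0 and 1.5).** Expected difference = 0.95 × (-0.50) = -0.475. Variances are 0.95 × 1.498 + 0.0475 × 1.00 = 1.471 and 0.95 × 1.498 + 0.0475 × 2.25 = 1.530. SE = √(3.001/127) = 0.154, the same to three decimals as with no zeroing, so a wider interval does not offset the shrinkage. P = 1 - Φ(1.96 - 0.025/0.154) = 3.6%.

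**The rule's own effect.** Recorded scores may also dilute, so the fair comparison is zeroing against recorded scores when violators carry none, half or all of the treatment difference. A simulation with a pooled t interval (4,000,000 trials per cell, no centre term) gives:

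| f | False non-inferiority, zeroed | Added by the rule: none carried | half | all |
|---|---|---|---|---|
| 0 | 2.5% | – | – | – |
| 1% | 2.7% | 0 | 0.1 | 0.2 |
| 2% | 2.9% | 0 | 0.2 | 0.4 |
| 5% | 3.6% | 0 | 0.6 | 1.1 |
| 10% | 5.1% | 0 | 1.5 | 2.6 |

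The last three columns are percentage points.

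**Sensitivity to the assumptions.** Across SD 1.00 to 1.36 and comparator mean 1.0 to 2.0, the normal approximation gives false non-inferiority with zeroing of 3.5% to 3.9% at f = 5% and 4.7% to 6.0% at f = 10%. At zero true difference (SD 1.224, mean 1.5), power goes from 90.0% to 89.8%, 89.4% and 89.0% at f = 2%, 5% and 10%.

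**Chance split between arms.** At the margin, each zeroed diphenhydramine patient moves the difference by about +1.5/127 = +0.012, and each zeroed cetirizine patient by about -1.0/127 = -0.008. For an illustrative six zeroed patients (6/254 = 2.4%):

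| Cetirizine : diphenhydramine | False non-inferiority |
|---|---|
| 5:1 | 1.5% |
| 4:2 | 2.1% |
| 3:3 | 2.8% |
| 2:4 | 3.8% |
| 1:5 | 4.9% |

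An exact 3:3 split has probability 31%; 1:5 has about 9%.

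**The case against.** Several points on the other side stand.

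- **Size.** Protocol Section 4 says that "the study investigator or designee will verify all inclusion and exclusion criteria to ensure patient eligibility" before randomisation, so f is probably small. The 2.6-point figure needs f = 10% and violators who carry the whole treatment difference. A patient with another antihistamine already acting may show less than that, and the documents do not settle it.
- **Discretion.** A reader might infer that the sponsor may choose case by case whether to zero the two named kinds of patient. The text does not support that: both examples are worded as definite. Only the lead-in is open, so the doubt concerns violations that are not listed. Review before unblinding further limits selective use.
- **Conflict with SAP 9.6.** A reader might infer that 9.6 and 10.2 contradict each other for every violator. They do not. SAP 9.6 reaches only data up to discontinuation, so the overlap arises only if the 2-hour score came first. One may also read the specific rule as overriding the general one, but the SAP does not say so.
- **Per-protocol analysis.** A reader might infer that no analysis free of these patients is planned. SAP 9.4 already foresees a per-protocol analysis of the primary endpoint. What the visible text lacks is its margin and interval, and any statement that the claim depends on it. The rest of 11.1, section 11.2 and the redacted 9.9 may add to this.
- **The remedy.** Recorded scores do not remove dilution from wrong-disease patients.

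The direction in expectation remains, as do the uncoordinated rules.

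**Conclusion.** The point holds as a low-end minor one. With equal expected shares, which is reasonable because both violations precede treatment, zeroing shrinks a true deficit to (1-f) of its size and so favours non-inferiority in expectation. Compared with recorded scores, it adds 0 to 0.4 points of false non-inferiority at f of 1 to 2%. For wrong-disease patients it may add nothing.

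It would go too far to say that the rule always helps cetirizine or materially inflates the error rate. A chance split can push one trial either way, and the documents give no f to support a large effect. Confidence is high in the direction and low in the size, which rests on the back-solved SD, the assumed comparator mean and a two-sample interval without the centre term of SAP 9.7.

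**What to change.** 1. In the ITT primary analysis, use these patients' recorded baseline and 2-hour scores, subject to the rescue and early-discharge rules of SAP 9.1. Handle a missing 2-hour score by the same pre-stated method as for any other patient. SAP 9.1 covers only rescue and early discharge and SAP 9.6 names no method, so state one unless text not shown already does.
2. Keep set-to-zero as a labelled sensitivity analysis, with the number of affected patients by arm.
3. Report the per-protocol analysis foreseen in SAP 9.4 beside the ITT result, with the same margin and confidence interval, unless the SAP text not shown (the rest of 11.1, section 11.2, redacted 9.9) already does so.
4. State that the rule in item 1 takes precedence where SAP 9.6 and 10.2 overlap. Replace the open lead-in and the label of examples with a closed list of violations, fixed before unblinding.

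The cost is SAP wording and one extra table. No patients or procedures are added. A few discontinued violators may lack a 2-hour score, which is why item 1 needs a stated method.
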